5.7 Criteria for Removal from the Study

Treatment with study drugs is to be discontinued when any of the following occurs:

- Lack of therapeutic effect (any effort should be made to provide therapy to the patient in a safe way for at least 3-6 cycles for proper assessment of potential efficacy)
- Adverse event(s) that, in the judgment of the Investigator, may cause severe or permanent harm or which rule out continuation of study drug.
- Withdrawal of consent

- Lost to follow up
- Death
- Suspected pregnancy

6.0 CRITERIA FOR RESPONSE

Best overall response will be categorized according to the International Working Group Criteria¹¹:

Complete remission (CR): Requires all of the following in the absence of both transfusion and growth factor support:

- Bone marrow: Age-adjusted normocellularity; <5% blasts; ≤grade 1 MF[†] and
- Peripheral blood: Hemoglobin ≥10 g/dL and <UNL; neutrophil count ≥ 1.0 × 10⁹/L and <UNL;
- Platelet count ≥100 × 10⁹/L and <UNL; <2% immature myeloid cells[‡] and
- Clinical: Resolution of disease symptoms; spleen and liver not palpable; no evidence of EMH

Partial remission (PR):

- Peripheral blood: Hemoglobin ≥10 g/dL and <UNL; neutrophil count ≥1 × 10⁹/L and <UNL; platelet count ≥100 × 10⁹/L and <UNL; <2% immature myeloid cells and
- Clinical: Resolution of disease symptoms; spleen and liver not palpable; no evidence of EMH or
- Bone marrow: Age-adjusted normocellularity; <5% blasts; ≤grade 1 MF[†], and peripheral blood: Hemoglobin ≥8.5 but <10 g/dL and <UNL; neutrophil count ≥1 × 10⁹/L and <UNL; platelet count ≥50, but <100 × 10⁹/L and <UNL; <2% immature myeloid cells[‡] and
- Clinical: Resolution of disease symptoms; spleen and liver not palpable; no evidence of EMH

Clinical improvement (CI): The achievement of anemia, spleen or symptoms response without progressive disease or increase in severity of anemia, thrombocytopenia, or neutropenia[§]

Anemia response	Transfusion-independent patients: a ≥2.0 g/dL increase in hemoglobin level Transfusion-dependent patients: becoming transfusion-independent [¶]
Spleen response [#]	A baseline splenomegaly that is palpable at 5-10 cm, below the LCM, becomes not palpable** or

	A baseline splenomegaly that is palpable at >10 cm, below the LCM, decreases by $\geq 50\%^{**}$
	A baseline splenomegaly that is palpable at <5 cm, below the LCM, is not eligible for spleen response
Symptoms response	A $\geq 50\%$ reduction in the MPN-SAF TSS ^{††}

Progressive disease:

- Appearance of a new splenomegaly that is palpable at least 5 cm below the LCM or
- A $\geq 100\%$ increase in palpable distance, below LCM, for baseline splenomegaly of 5-10 cm or
- A 50% increase in palpable distance, below LCM, for baseline splenomegaly of >10 cm or
- Leukemic transformation confirmed by a bone marrow blast count of $\geq 20\%$ or
- A peripheral blood blast content of $\geq 20\%$ associated with an absolute blast count of $\geq 1 \times 10(9)/L$ that lasts for at least 2 weeks

Stable disease: Belonging to none of the above listed response categories

Relapse:

- No longer meeting criteria for at least CI after achieving CR, PR, or CI, or
- Loss of anemia response persisting for at least 1 month or
- Loss of spleen response persisting for at least 1 month
- Recommendations for assessing treatment-induced cytogenetic and molecular changes.

Cytogenetic remission

At least 10 metaphases must be analyzed for cytogenetic response evaluation and requires confirmation by repeat testing within 6 months window
 CR: eradication of a preexisting abnormality
 PR: $\geq 50\%$ reduction in abnormal metaphases
 (partial response applies only to patients with at least ten abnormal metaphases at baseline)

Molecular remission

Molecular response evaluation must be analyzed in peripheral blood granulocytes and

requires confirmation by repeat testing within 6 months window
CR: Eradication of a pre-existing abnormality
PR: $\geq 50\%$ decrease in allele burden (partial response applies only to patients with at least 20% mutant allele burden at baseline)

Cytogenetic/molecular relapse

Re-emergence of a pre-existing cytogenetic or molecular abnormality that is confirmed by repeat testing

EMH, extramedullary hematopoiesis (no evidence of EMH implies the absence of pathology- or imaging study-proven nonhepatosplenic EMH); LCM, left costal margin; UNL, upper normal limit.

**Baseline and post treatment bone marrow slides are to be interpreted at one sitting by a central review process. Cytogenetic and molecular responses are not required for CR assignment.*

[†]Grading of MF is according to the European classification: Thiele et al. European consensus on grading bone marrow fibrosis and assessment of cellularity. Haematologica. 2005;90:1128. It is underscored that the consensus definition of a CR bone marrow is to be used only in those patients in which all other criteria are met, including resolution of leukoerythroblastosis. It should also be noted that it was a particularly difficult task for the working group to reach a consensus regarding what represents a complete histologic remission.

[‡]Immature myeloid cells constitute blasts + promyelocytes + myelocytes + metamyelocytes + nucleated red blood cells. In splenectomized patients, <5% immature myeloid cells is allowed.

[§]See above for definitions of anemia response, spleen response, and progressive disease. Increase in severity of anemia constitutes the occurrence of new transfusion dependency or a ≥ 20 g/L decrease in hemoglobin level from pretreatment baseline that lasts for at least 12 weeks. Increase in severity of thrombocytopenia or neutropenia is defined as a 2-grade decline, from pretreatment baseline, in platelet count or absolute neutrophil count, according to the Common Terminology Criteria for Adverse Events (CTCAE) version 4.0. In addition, assignment to CI requires a minimum platelet count of $\geq 25\,000 \times 10(9)/L$ and absolute neutrophil count of $\geq 0.5 \times 10(9)/L$.

^{||}Applicable only to patients with baseline hemoglobin of <100 g/L. In patients not meeting the strict criteria for transfusion dependency at the time of study enrollment (see as follows), but have received transfusions within the previous month, the pretransfusion hemoglobin level should be used as the baseline.

[¶]Transfusion dependency before study enrollment is defined as transfusions of at least 6 units of packed red blood cells (PRBC), in the 12 weeks prior to study enrollment, for a hemoglobin level of <85 g/L, in the absence of bleeding or treatment-induced anemia. In addition, the most recent transfusion episode must have occurred in the 28 days prior to study enrollment. Response in transfusion-dependent patients requires absence of any PRBC transfusions during any consecutive “rolling” 12-week interval during the treatment phase, capped by a hemoglobin level of ≥ 85 g/L.

#In splenectomized patients, palpable hepatomegaly is substituted with the same measurement strategy.

***Spleen or liver responses must be confirmed by imaging studies where a ≥35% reduction in spleen volume, as assessed by MRI or CT, is required. Furthermore, a ≥35% volume reduction in the spleen or liver, by MRI or CT, constitutes a response regardless of what is reported with physical examination.*

††Symptoms are evaluated by the MPN-SAF TSS.¹⁷ The MPN-SAF TSS is assessed by the patients themselves and this includes fatigue, concentration, early satiety, inactivity, night sweats, itching, bone pain, abdominal discomfort, weight loss, and fevers. Scoring is from 0 (absent/as good as it can be) to 10 (worst imaginable/as bad as it can be) for each item. The MPN-SAF TSS is the summation of all the individual scores (0-100 scale). Symptoms response requires ≥50% reduction in the MPN-SAF TSS.

##Progressive disease assignment for splenomegaly requires confirmation by MRI or computed tomography showing a ≥25% increase in spleen volume from baseline. Baseline values for both physical examination and imaging studies refer to pretreatment baseline and not to posttreatment measurements.

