5.5 Pretreatment Evaluation

- History and physical exam including vital signs, body weight and height, and spleen and liver measurements. This also includes a transfusion history for 3 months prior to day 1 and concomitant medication notation (within 14 days of study day 1)
- CBC and differential, electrolytes (Na, K, Cl, Mg, HCO3), creatinine, uric acid, BUN, glucose, total and direct bilirubin, and SGPT, PT/PTT, INR (within 14 days of study day 1).
- Bone marrow biopsy and aspirate (within 1 month of study day 1, or within 3 months of study day 1 if patient was not on any therapy).
- ECG (within 14 days of study day 1)
- Pregnancy test (for FCBP only) within 7 days of study day 1
- Myeloproliferative Neoplasm Symptom Assessment Form Total Symptom Score (MPN-SAF TSS) questionnaire

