5.6 Evaluation During Study

- Directed history and physical examination including vital signs, body weight, and spleen and liver measurements once each cycle on cycles 2-7, then once every 3 cycles (C10, C13, C16, ...). This also includes a transfusion history for previous cycle of therapy and concomitant medication notation. Spleen and liver measurements will be obtained by the physicians or physician assistants during the clinic visit and documented in the medical record.
- CBC and differential, electrolytes (Na, K, Cl, Mg, HCO3), creatinine, BUN, glucose, total bilirubin, and SGPT every 2 weeks for 6 cycles, then CBC with differential every cycle and electrolytes (Na, K, Cl, Mg, HCO3), creatinine, BUN, glucose, total bilirubin, and SGPT every 3 cycles and as deemed appropriate while on therapy. Therapy also includes the first 3 months of ruxolitinib alone.
- ECG will be performed prior to the first cycle of pracinostat (C4), then once during cycles 5 and 6, then every 3 cycles starting with cycle 10 (specifically, ECG should be performed approximately 90 minutes post pracinostat dosing on the day of visit to MD Anderson)
- Bone marrow aspiration and biopsy after cycles 6 (+/- 10 days) and 12 (+/- 10 days), and if deemed appropriate by the investigator, every 6 cycles after cycle 12.
- Response assessment after cycle 3 and cycle 6, then every 6 cycles. Assessment may not include bone marrow biopsy on all occasions.
- Collect any unused study drug and review patient study drug dosing diary for compliance during each cycle for the first 7 cycles then every 3 cycles.
- Continuous assessment of AEs
- Myeloproliferative Neoplasm Symptom Assessment Form Total Symptom Score (MPN-SAF TSS) questionnaire during each cycle for the first 7 cycles then every 3 cycles.

Every effort will be made to adhere to the schedule of events and all protocol requirements within the +/- 10 day window. Variations in schedule of events and other protocol requirements that do not affect the rights and safety of the patient will not be considered as deviations. Such variations may include laboratory assessments completed outside of schedule, occasional missed required research samples such as PK or PD. All dose adjustments will be made according to the protocol unless discussed with the PI and do not exceed the dosages described in the protocol.

Outside Physician Participation During Treatment

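### Spleen response and spleen progression need MRI/CT volumes from a pretreatment baseline, but the evaluation lists contain no scan; the baseline for patients already on ruxolitinib is unreconciled, and the CI platelet floor carries a unit error

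*Combined protocol and SAP*

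**What the plan says.** **Response criteria.** Section 8.0 defines the primary endpoint as CI, PR or CR by the IWG criteria. Section 6.0 defines CI as "The achievement of anemia, spleen or symptoms response without progressive disease" and without worsening cytopenias. For the spleen route, the palpation rule depends on baseline size: "A baseline splenomegaly that is palpable at 5-10 cm, below the LCM, becomes not palpable", whereas a spleen above 10 cm must shrink by at least half. Two footnotes add imaging:

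- "Spleen or liver responses must be confirmed by imaging studies", with at least a 35% volume reduction by MRI or CT. The same reduction also counts as a response whatever palpation shows.
- "Progressive disease assignment for splenomegaly requires confirmation by MRI or computed tomography", with at least a 25% volume increase.

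The baseline rule is "Baseline values for both physical examination and imaging studies refer to pretreatment baseline and not to posttreatment measurements".

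**Evaluations.** Section 5.5 lists "History and physical exam including vital signs, body weight and height, and spleen and liver measurements", then laboratory tests, marrow, ECG, pregnancy test and the symptom questionnaire. Section 5.6 says "Spleen and liver measurements will be obtained by the physicians or physician assistants during the clinic visit". Neither section, nor any other, schedules an MRI or CT.

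**Patients already on ruxolitinib.** Section 4.0 admits patients with less than 3 months of current ruxolitinib. Section 5.0 credits that time toward the three monotherapy cycles. The windows in Section 5.5 are set around study day 1.

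**Platelet floor.** The CI footnote prints a minimum platelet count of 25 000 × 10⁹/L, beside a neutrophil minimum of 0.5 × 10⁹/L.

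**The concern.** A percentage change in volume needs two scans. A follow-up scan might still be arranged when a response is suspected, but a pretreatment scan that was not taken cannot be recovered. Every patient enters with a spleen palpable at 5 cm or more (Section 4.0), so the spleen route to CI is open to all 25.

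The consequences run both ways. A palpated spleen response without paired scans is not confirmed, which lowers the response rate. Palpated spleen progression without paired scans cannot be assigned, so a patient with an anemia or symptoms response may stay in CI, which raises it. The same rate drives the futility rule, and loss of spleen response is one of the definitions of relapse. Section 8.0 counts early drop-outs as failures but gives no rule for a patient still on study without paired scans. Two assessors could score the same patient differently.

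**Working it through.** **1. Requirements against lists**

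| Item | Needed under Section 6.0 | Listed in 5.5 or 5.6 |
|---|---|---|
| Palpated spleen size, before and on treatment | yes | yes |
| MRI/CT volume before treatment | yes | no |
| MRI/CT volume on treatment | yes | no |
| Symptom score and hemoglobin | yes | yes |

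Anemia and symptoms responses need no scan. Leukemic transformation, the other form of progression, needs none either.

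**2. The plan's own figures**

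Inputs from Section 8.0: N = 25; looks at 5, 10, 15 and 20; beta(1,1) prior; stop if Pr(OR rate < 0.5) > 0.95. With x responders in n, the posterior is beta(1 + x, 1 + n − x). The largest x that stops is 0, 2, 4 and 6, as in Table 1. Adding the toxicity rule (beta(0.4, 1.6) prior, cut-off 0.87) reproduces all 16 early-stop probabilities in Table 2 to within about 0.01, for example 0.131 against 0.13 (OR 0.5, toxicity 0.1) and 0.354 against 0.35 (OR 0.4, toxicity 0.1). The design arithmetic is sound.

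**3. Sensitivity of the endpoint**

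- One patient: 1/25 = 4 points. The beta(1,1) 95% credible interval is 0.334–0.701 at 13/25 and 0.299–0.666 at 12/25.
- Futility rule alone at a true 50%: first-crossing probabilities at the four looks are 0.0312 + 0.0391 + 0.0264 + 0.0180 = 0.115.
- At a true 50%, 19.8% of trials never stop but come within exactly one responder of doing so; one response lost by that look would stop them. Another 10.4% stop exactly on the boundary; one more response by that look would have averted that stop.
- Assumed loss: if 20% of responders are spleen-only and unconfirmed, the scored rate is 0.50 × (1 − 0.20) = 0.40 and the crossing probability is 0.342.
- Assumed gain: if unassigned progression adds 5 or 10 points, the scored rate is 0.55 or 0.60 and the crossing probability is 0.057 or 0.026.
- A 10-point loss and a 10-point gain cancel, leaving 0.115.

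**4. Baseline for patients already on ruxolitinib (hypothetical patient)**

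Take a spleen at 12 cm before ruxolitinib, 8 cm at study day 1 and 5 cm after cycle 6. Against 12 cm the decrease is 7/12 = 58%, which meets the palpation criterion. Against 8 cm the spleen would have to become impalpable, so the criterion is not met. For volume, if 20% had already gone before study day 1, the further reduction needed is 1 − 0.65/0.80 = 19% against the pre-ruxolitinib value and 35% against study day 1.

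**5. Platelet floor**

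25 000 per µL = 25 × 10⁹/L, and 25 000/25 = 1000. The printed value is 25 000/100 = 250 times the CR floor and 25 000/50 = 500 times the entry minimum. Read literally, no patient could be CI.

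**The case against.** **The lists are not exhaustive.** JAK2V617F allele burden is analysed in Section 8.0 but appears in neither list. Section 5.6 also says "Every effort will be made to adhere to the schedule of events and all protocol requirements", and its response assessment can be read to include whatever Section 6.0 requires. This stands in part: the documents do not show that no scan will be done, and the supplied text has no separate schedule table to consult. But nothing tells a site to obtain a scan before treatment.

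**The baseline is not undefined.** A reader might infer that it is. That goes too far: Section 5.5 is headed as the pretreatment evaluation and is anchored to study day 1, so an enrolment baseline is a natural reading. What remains is narrower. For patients already on ruxolitinib, that anchor falls after treatment began, which the baseline footnote rules out.

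**The endpoint is not lost.** A reader might infer that the response rate cannot be assessed, or that it is biased downward. Neither follows. CI can be reached without a scan, and unassigned progression pushes the other way.

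**Deleting the imaging footnotes is not a neutral repair.** This stands. Section 6.0 holds the only definition of progression, and Section 5.0 makes progression a reason to end treatment. Removing the imaging-only route would also replace the IWG endpoint the sponsor chose.

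**The platelet figure is an evident slip.** Agreed, and nobody is likely to apply it literally. It still sits inside the primary endpoint definition.

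**Conclusion.** The point holds. Section 6.0 and Sections 5.5–5.6 do not agree on what is collected to score spleen response and spleen progression; the baseline for patients already on ruxolitinib is unreconciled; and the CI platelet floor is wrong as printed.

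Only the 4 points per reclassified patient, the 0.115 and 19.8% at a true 50%, and the platelet ratios rest on no assumption about scans. The 0.342, 0.057 and 0.026 rest on assumed shares of spleen-only responders and of CI candidates with palpated progression, which the documents do not give. These are futility-only figures; with the toxicity rule at a true toxicity rate of 0.1, Table 2 gives 0.13 at a response rate of 50% and 0.35 at 40%. The net effect could have either sign. That 25 × 10⁹/L is the intended floor is inferred from the unit conversion and from Sections 5.1 and 5.2, which pair platelets of 25 × 10⁹/L with neutrophils of 0.5 × 10⁹/L.

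**What to change.** 1. **Reconcile Section 6.0 with Sections 5.5–5.6 for scoring the primary endpoint.** The sponsor chooses one of two routes.
   - List the pretreatment and follow-up scans that Section 6.0 already requires, and say how a patient without paired scans is scored. This keeps the IWG definition. It adds procedures to the evaluation lists and cannot help patients already treated without a pretreatment scan.
   - State in Section 8.0 that spleen response is scored by palpation for every patient, say how unconfirmed spleen progression is handled when CI is scored, and label the rate *modified IWG-MRT, not imaging-confirmed*. This costs wording only. The result is less comparable with imaging-confirmed rates, and a patient who responds by imaging alone would no longer count.

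   Either way, limit the change to endpoint scoring. How progression is established for ending treatment (Sections 5.0 and 6.0) is for the sponsor to reconcile separately.
2. **Name one baseline time point**, before ruxolitinib or study day 1, for patients who enter on ruxolitinib. Use it for spleen, hemoglobin, platelets and neutrophils throughout Section 6.0. One sentence suffices; a pre-ruxolitinib choice depends on records made before enrolment.
3. **Correct the unit of the CI platelet floor.** The evident intent is 25 × 10⁹/L (25 000 per µL), for the sponsor to confirm. This costs nothing.

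None of these changes alters the planned N, the Table 1 boundaries or Table 2.

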7.0 REGULATORY AND REPORTING REQUIREMENTS

7.1 Adverse Event Reporting for MD Anderson-Sponsored IND Protocols

All adverse events that are possible, probably or definitely related to the study treatment will be captured on the case report form. Any grade 3 or higher adverse event that is considered unrelated or unlikely related to the study treatment will also be recorded. Adverse events will be defined using NCI CTCAE version 4.0.

All adverse events occurring between the time the subject is consented and begins study drug will be considered a baseline event and recorded. Baseline adverse events will be recorded in the case report form in prior medical history. All baseline adverse events that increase in severity during the course of treatment will be captured as an adverse event in the case report form.

Any adverse event that occurs during the study period (up through 30 days after the last day drug is administered) will be followed until clinical recovery is complete and laboratory tests have returned to normal, until progression of the event has been stabilized, or until the PI determines there has been acceptable resolution of the event.

7.2 Serious Adverse Event Reporting (SAE) for M. D. Anderson-Sponsored IND Protocols

An adverse event or suspected adverse reaction is considered “serious” if, in the view of either the investigator or the sponsor, it results in any of the following outcomes:

- Death
- A life-threatening adverse drug experience – any adverse experience that places the patient, in the view of the initial reporter, at immediate risk of death from the

adverse experience as it occurred. It does not include an adverse experience that, had it occurred in a more severe form, might have caused death.

- Inpatient hospitalization or prolongation of existing hospitalization
- A persistent or significant incapacity or substantial disruption of the ability to conduct normal life functions.
- A congenital anomaly/birth defect.

Important medical events that may not result in death, be life-threatening, or require hospitalization may be considered a serious adverse drug experience when, based upon appropriate medical judgment, they may jeopardize the patient or subject and may require medical or surgical intervention to prevent one of the outcomes listed in this definition. Examples of such medical events include allergic bronchospasm requiring intensive treatment in an emergency room or at home, blood dyscrasias or convulsions that do not result in inpatient hospitalization, or the development of drug dependency or drug abuse (21 CFR 312.32).

- Important medical events as defined above may also be considered serious adverse events. Any important medical event can and should be reported as an SAE if deemed appropriate by the Principal Investigator or the IND Sponsor, IND Office.
- All events occurring during the conduct of a protocol and meeting the definition of a SAE must be reported to the IRB in accordance with the timeframes and procedures as per “The University of Texas M. D. Anderson Cancer Center Institutional Review Board Policy for Investigators on Reporting Unanticipated Adverse Events for Drugs and Devices”. Unless stated otherwise in the protocol, all SAEs, expected or unexpected, must be reported to the IRB, regardless of attribution (within 5 working days of knowledge of the event).
- All life-threatening or fatal events, that are unexpected, and related to the study drug, must have a written report submitted within 24 hours (next working day) of knowledge of the event to the Safety Project Manager in the IND Office.
- Unless otherwise noted, the electronic SAE application (eSAE) will be utilized for safety reporting to and MDACC IRB.
- Serious adverse events will be captured from the time of the first protocol-specific intervention, until 30 days after the last dose of drug, unless the participant withdraws consent. Serious adverse events must be followed until clinical recovery is complete and laboratory tests have returned to baseline, progression of the event has stabilized, or there has been acceptable resolution of the event.
- Additionally, any serious adverse events that occur after the 30 day time period that are related to the study treatment must be reported to the IND Office. This may include the development of a secondary malignancy.

Reporting to FDA:

Serious adverse events will be forwarded to FDA by the IND Sponsor (Safety Project Manager IND Office) according to 21 CFR 312.32. It is the responsibility of the PI and the research team to ensure serious adverse events are reported according to the Code of Federal Regulations, Good Clinical Practices, the protocol guidelines, the sponsor's guidelines, and Institutional Review Board policy.

